5.2.5. Direct cost

Direct costs are costs related to the health care system and are divided into health and non-healthcare costs. By definition, **direct health costs** include hospital costs, outpatient costs, tests costs, treatment costs, etc., while **direct non-health costs** include transport costs, social services costs, essential adaptations of the patient's home costs, etc. Therefore, this study will be considered:

- **Direct health costs:**

- Number of primary care visits due to IPF (T6, T12, acute exacerbations)
- Number of secondary care visits due to IPF (pneumologist, nurse, nutritionist, psychiatrist, psychologist, respiratory rehabilitation, pneumologist home visit, nursing home visit, smoking consult cessation, other health professional) (T6, T12, acute exacerbations)
- Number of emergency visits (primary care and hospital) due to IPF (T6, T12, acute exacerbations)
- Number of hospitalizations due to IPF (time in emergency room, number of days in plant, number of days in ICU) (T6, T12, acute exacerbations)
- Number of outpatient tests due to IPF (T6, T12, acute exacerbations):
 - Laboratory test (hemogram, biochemistry, coagulation profile, erythrocyte sedimentation rate, liver profile, angiotensin converting enzyme, rheumatoid factor, antinuclear antibodies, another tests).
 - Pulmonary function test (spirometry, pulmonary plethysmography, carbon monoxide diffusion capacity, 6-minute walk test, another test).
 - Other examinations (x-Ray, high resolution computed tomography, bronchoscopy, bronchoalveolar lavage, transbronchial biopsy, lung cryobiopsy, surgical lung biopsy, arterial blood gases, another test).
- Non-pharmacological treatment due to IPF (liquid oxygen therapy, electric portable oxygen therapy, oxygen therapy concentrator, oxygen, oxygen therapy portable device, high flow nasal cannulas, non-invasive mechanical ventilation) (T6, T12, acute exacerbations).
- Pharmacological treatments due to IPF (except treatments administered in hospitalization) (T6, T12, acute exacerbations).

- **Direct non-health costs:**

- Transport (number of trips and km of displacement in taxi, number of trips and km of displacement in ambulance) (T6, T12, acute exacerbations).
- Formal caregiver (time dedicated to patient care with IPF) (T6, T12, acute exacerbations).

- Orthopaedic material (manual wheelchair, electric wheelchair, anti-bedsore cushion, orthopaedic bed, orthopaedic chair, other) (T12, acute exacerbations).

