- Economic aid and formal social services (T12, acute exacerbations)
- Structural adaptations (change in the structure of housing, elevators on the stairs in common areas, complementary technical aids, vehicle adaptation, other) (T12, acute exacerbations).

Calculation of direct health costs

Visits: The cost of visits will be calculated by multiplying the number of visits (emergency, medical) by the corresponding unit cost, which will depend on the health care area (primary or secondary) in which the visit occurred.

Hospitalizations: To calculate the cost of hospitalizations, days of stay in each unit (ICU, ward) will be multiplied by the unit cost corresponding to each unit. The sum of the costs of each service will then be calculated. In addition, emergency room admission will be added: if length of emergency stay was “less than 24 hours”, emergency room visit cost will be considered; if length of emergency stay was “more than 24 hours”, one day of emergency stay cost will be considered. Data on intubation during hospitalization (yes/no) will be used as qualitative information and not calculated as a cost.

Outpatient tests and non-pharmacological treatment: The cost of outpatient tests and non-pharmacological treatment will be obtained by multiplying the natural units of resource use (number of tests) by the unit cost of each outpatient test.

Pharmacological treatment: The costs of pharmacological treatment will be calculated taking into account:

- **Pharmacological doses**

The total dose prescribed of each active ingredient during the last 6 months will be calculated by multiplying the dose prescribed by the time on treatment. The time on treatment will be determined according to the start and end date of treatment. The scheduled dose may be daily, twice a day, three times a day, alternate days, weekly, every 2 weeks, monthly or on demand. If the schedule dose is ‘*on demand*’ an average dose according to the technical data sheet will be calculated.

The calculations described above will provide the total dose that each patient has received for the observational period.

- **Costs**

For treatments dispensed in the pharmacy office, the unit costs for each treatment were calculated taking into account the retail price (RRP) plus value added tax (VAT). From the National Health System (NHS) perspective, the co-payment of the Spanish Royal Decree-Law 16/2012 will be applying:

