- Reduced contribution medication: 10% of the retail price for medication belonging to ATC groups qualifying for reduced contribution, with a maximum contribution expressed in euros. For reduced contribution medicines with a maximum of €4.26 per package.
- Normal contribution medicines: copayment in this medicines group should be applied according to each individual situation and on declared annual income:

Medicines Co-payment	
Annual resident tax declaration	Patient's copayment
Income \geq 100.000 €	60%
Income 18.000-100.000 €	50%
Income $<$ 18.000 €	40%
Pensioners	10%
Civil servant	30%

The cost of each pharmacological treatment will be obtained by multiplying the total dose (taking into account the prescribed dose and the administration schedule) each patient has received for the observational period by the unit cost of each treatment. If the commercial brand and presentation are available, the unit costs will be those that correspond to the said commercial brand and presentation. If this information is not available, an average cost will be calculated taking into account all commercialized presentations.

The annual direct health cost will be calculated as the sum of the costs of medical visits, emergency room visits, hospital admissions, outpatient tests, non-pharmacological treatments, and pharmacological treatments.

Calculation of direct non-health costs

Transport: The cost of ambulances will be obtained by multiplying the number of trips made per unit cost. For journeys by taxi, the kilometres recorded for each journey will be multiplied by the total cost of journeys made during the observation period, and the result will be multiplied by the corresponding unit cost.

Paid caregivers: The cost of paid caregivers will be calculated by multiplying the number of hours per day of care given by the number of days. The result will be the number of hours of paid care during the observational period, and will be multiplied by the corresponding unit cost.

Orthoprosthetic material: The cost of technical aids will be calculated by multiplying the number of days the patient has required the aid by the daily cost, calculated according to the catalogues of orthoprosthetic benefits of the autonomous communities.

Financial aid and social services: The cost registered in the eCRF will be considered. The monthly cost will be multiplied by the time aid was received. If the monthly amount is 'unknown', the mean cost of patients with full data will be used.

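### SAP 5.2.5 has no rule to stop an emergency attendance that ends in admission from being charged in both the visits line and the hospitalization line

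*SAP*

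**What the plan says.** Four parts of SAP 5.2.5 bear on this.

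- **Resource list, emergency visits.** The item is "Number of emergency visits (primary care and hospital) due to IPF", with no limit to visits that end in discharge.
- **Resource list, hospitalizations.** Emergency time appears again here: "Number of hospitalizations due to IPF (time in emergency room, number of days in plant, number of days in ICU".
- **Costing rules.** For visits, "The cost of visits will be calculated by multiplying the number of visits (emergency, medical) by the corresponding unit cost". For hospitalizations, ward and ICU days are priced, and then "In addition, emergency room admission will be added: if length of emergency stay was “less than 24 hours”, emergency room visit cost will be considered". For an emergency stay above 24 hours, "one day of emergency stay cost will be considered".
- **Summation.** "The annual direct health cost will be calculated as the sum of the costs of medical visits, emergency room visits, hospital admissions", followed by the remaining direct health items.

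The Protocol does not add a rule. Section 9.3.2.1 lists emergency visits and hospitalizations as separate items. Section 9.4 has the investigator reconcile the patient diary with the medical records, which is a different check from comparing emergency visits with admissions.

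**The concern.** A patient who attends a hospital emergency department because of IPF and is then admitted fits both resource items as worded. For an emergency stay under 24 hours, the same unit cost, that of an emergency visit, is named in both costing rules, and both results enter the annual direct health cost.

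The SAP draws inpatient boundaries elsewhere in the same section: drugs given during a hospital stay are excluded, and the tests counted are outpatient ones. Emergency visits have no such boundary. Two analysts working from this text could program the primary cost variable differently. The same items are also used to cost acute exacerbations, so the exacerbation cost table is exposed as well.

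The treatment of long emergency stays raises a smaller question that runs in the opposite direction. Any stay above 24 hours is longer than the single day charged for it.

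**Working it through.** The documents give no unit costs, admission counts or lengths of stay, so there is no stated figure to reproduce. What can be checked is the cost identity and the size of the overlap under stated assumptions.

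**Cost identity as worded in SAP 5.2.5**

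Direct health cost = (emergency visits × visit cost) + sum over admissions of (ward days × ward cost + ICU days × ICU cost + emergency charge) + other items.

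The emergency charge is one visit cost for an emergency stay under 24 hours and one emergency-day cost for a stay over 24 hours.

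**Assumed inputs (not in the documents), in units of one ward day**

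- r, cost of an emergency visit: 0.2 to 0.5
- e, cost of an emergency day: 0.5 to 1.0
- L, ward days: 5 to 12, with no ICU days (ICU days would lower the percentages)
- d, true length of an emergency stay over 24 hours: 1.5 to 3 days

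**Step 1. Emergency stay under 24 hours**

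Charged once, the admission costs L + r. Charged in both lines, it costs L + 2r. The excess is r, or r / (L + r) as a share.

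- Smallest: L = 12, r = 0.2 gives 0.2 / 12.2 = 1.6%.
- Largest: L = 5, r = 0.5 gives 0.5 / 5.5 = 9.1%.
- If the attendance is recorded only under the admission, the excess is 0.

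**Step 2. Emergency stay over 24 hours, single-day charge**

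Costing the full stay gives L + d·e; the SAP gives L + e. The relative difference is (L + e) / (L + d·e) − 1.

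- Smallest: L = 12, e = 0.5, d = 1.5 gives 12.5 / 12.75 − 1 = −2.0%.
- Largest: L = 5, e = 1.0, d = 3 gives 6 / 8 − 1 = −25.0%.

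**Step 3. Both effects in one admission**

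If the visit is also charged in the visits line, the relative difference is (L + e + r) / (L + d·e) − 1. The pairs (r, e) tried were (0.2, 0.5), (0.5, 0.5) and (0.5, 1.0), at L = 5 and 12 and d = 1.5, 2 and 3.

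- Lowest: L = 5, r = 0.5, e = 1.0, d = 3 gives 6.5 / 8 − 1 = −18.8%.
- Highest: L = 5, r = 0.5, e = 0.5, d = 1.5 gives 6 / 5.75 − 1 = +4.3%.

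For long emergency stays the two effects therefore work against each other, and the net sign depends on the inputs.

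**The case against.** The strongest reply is that double charging depends on data entry that the documents do not show. Emergency time is a field within the hospitalization item. A reasonable form design would record attendances leading to admission there and keep the emergency-visit item for the rest. On that reading the emergency charge inside the hospitalization line is needed, because the attendance is priced nowhere else. This stands as a possibility, and it is why the excess may be zero. It does not remove the point, because the reading needs an exclusion that neither document states. Protocol 9.8 also plans no regular source data verification that might expose inconsistent entry.

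A reader might make three stronger inferences that the documents do not support.

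- **That every admission carries an extra emergency charge.** The SAP chooses the charge by length of emergency stay and does not say that an admission without one is charged.
- **That the overlap widens the cost gap between FVC groups.** Protocol section 7 links low FVC to exacerbations and expects higher cost, but it gives no share of emergency visits ending in admission for any group. Any figure for a distorted between-group ratio would rest on invented shares.
- **That the single-day charge is an error.** The SAP puts the two durations in quotation marks, as if they were response categories. If hours were not collected, some fixed charge is unavoidable, and the SAP discloses the one it uses.

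It is also fair to say that the effect on total annual cost may be small where drug cost dominates, and that SAP 5.2.6.2 treats all tests as exploratory.

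**Conclusion.** The gap in the rule is real: both lines carry an emergency charge, both enter the sum, and nothing in either document separates them. On the wording alone, an emergency attendance that ends in admission is priced twice. Whether this happens in the data depends on the eCRF, so it follows from the text but is not an established fact.

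The excess is one emergency-visit cost per affected admission. The range of 1.6% to 9.1% is a share of a single admission's cost, not of annual cost, and rests on the cost ratios and lengths of stay assumed above. No euro amount can be derived, and neither the size nor the direction of any effect on the FVC-group contrast can be derived.

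The single-day charge is a lower bound for stays over 24 hours. It supports a sensitivity run and no more. The wording should be settled before the analysis because it defines a component of the primary outcome and is cheap to settle.

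**What to change.** 1. In SAP 5.2.5, state that the visits line costs only emergency visits that did not end in hospital admission, and that attendances ending in admission are costed once, in the hospitalization line. If the eCRF already enforces this, say so and cite the form.
2. If the collected counts cannot separate the two kinds of visit, add a sensitivity analysis. For each patient, subtract one emergency-visit cost per admission with an emergency stay, up to the number of hospital emergency visits recorded: visit cost × min(admissions with an emergency stay, hospital emergency visits). This needs counts only. Matching by date should not be assumed feasible, because the SAP describes emergency visits as a number.
3. For emergency stays over 24 hours, if only the category is recorded, keep the single-day charge, describe it as a lower bound, and add a run at two days.

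The cost is one or two sentences in the SAP and up to two short sensitivity runs. None of this needs new data, provided that hospital emergency visits can be told apart from primary-care ones. The SAP implies that they can, since it prices visits by care area.

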### **9.7.1 Main analysis**

*a)* To compare the economic impact of Idiopathic Pulmonary Fibrosis (IPF) according to predicted FVC% (FVC<50%, FVC 50-80%, FVC>80%), in adult patients through the estimation of annual direct and indirect costs associated with the disease.

Annual direct IPF-related costs (primary and secondary care visits, outpatient visits, emergency visits -primary care and hospital-, hospitalisations, ICU with and without intubation, outpatient tests and other examinations, pharmacological and non-pharmacological treatments, orthopedic material, use of transport, formal caregiver, formal social services, economic aid and structural adaptations) and indirect costs (days off work and informal caregiver) will be quantified for each patient over the follow-up period of 12 month.

The direct costs over the 12 month follow-up period will be quantified by multiplying the recorded natural units of use of resources by the unit costs obtained by consulting Spanish databases or similar studies. The opportunity cost method will be used to calculate informal care costs. The indirect costs will be estimated by applying salary costs based on the latest data published by the Spanish Instituto Nacional de Estadística (INE) (6) from the salary structure survey, adjusted to age.

In order to obtain the most recent unit costs, they will be consulted at the time of the analysis. All costs will be expressed in euros for the year 2018, updating as necessary the costs from previous periods according to the cumulative consumer price index (CPI) since the publication of the cost up to December 31, 2017.

For the primary objective of the study, the characteristics of the subpopulations defined by the categorisation of the deterioration in predicted FVC (FVC <50%, FVC 50-80%, FVC >80%) at the time of inclusion (T=0) will be described. The Chi-square test will be used for the comparisons of the qualitative (categorical) variables. For the comparisons of the quantitative (continuous) variables, analysis of variance (ANOVA) or Kruskal-Wallis tests will be performed. Results of all statistical tests must be interpreted purely exploratorily.

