Structural changes: The cost registered in the eCRF will be considered.

Direct non-health costs will be calculated as the sum of transport costs, paid caregivers costs, orthoprosthetic material costs, financial aid and social services costs, and structural changes costs.

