5.2.6.1 Total cost

In the analysis from the social perspective, the total costs will be obtained as the sum of the direct health costs (without co-payment), direct non-health costs and indirect costs.

In the analysis from the perspective of the Spanish NHS, health costs will be direct health costs and direct non-health cost considering only the part financed by the NHS.

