5.2.6.2 Unit cost

The following unit costs and cost data sources will be used:

- Hospitalizations, emergency room visits, medical visits, outpatient tests, and non-pharmacological treatments: the unit costs will be established from the representative national rates collected in the ESALUD Spanish health costs database.
- Pharmacological treatments: prices published in the Drug Database of the General Council of Official Associations of Pharmacists.
- Lost productivity: wage/salary costs will be calculated according to the latest data published by the Spanish National Statistics Institute on the survey of the salary structure.

In order to obtain the most recent unit costs, they will be consulted at the time of the analysis. All costs will be expressed in euros for the year in which the analysis is performed, updating as necessary the costs from previous periods according to the cumulative consumer price index (CPI).

For the primary objective of the study, the characteristics of the subpopulations defined by the categorisation of the deterioration in predicted FVC (FVC <50%, FVC 50-80%, FVC >80%) at the time of inclusion (T=0) will be described by means of: mean, SD, 95% CI of the mean, median, IQR (P25-P75), max. and min. The CI of the costs will be calculated using bootstrapping techniques using replacement samples of the same size as the original sample. In total 10 000

simulations will be made and the 2.5 and 97.5 percentiles of the distribution will be used to determine the 95% CI.

Analysis of variance (ANOVA) or Kruskal-Wallis tests will be performed to compare the direct and indirect costs by subpopulation (FVC <50%, FVC 50-80%, FVC >80%). Results of all statistical tests must be interpreted purely exploratorily.

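### The SAP taxi formula does not yield euros, and the full-year charge for a missing treatment start date can overstate cost because it ignores the visit record

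*SAP*

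**What the plan says.** **Taxi.** SAP section 5.2.5 lists the taxi data as "number of trips and km of displacement in taxi". Its calculation paragraph says that "the kilometres recorded for each journey will be multiplied by the total cost of journeys made during the observation period", and then applies a unit cost to the product. The sentence just before handles ambulances differently: "The cost of ambulances will be obtained by multiplying the number of trips made per unit cost". The general rule for direct costs in Protocol section 9.7.1 is "multiplying the recorded natural units of use of resources by the unit costs obtained by consulting Spanish databases or similar studies". The unit-cost list in SAP section 5.2.6.2 opens with "Hospitalizations, emergency room visits, medical visits, outpatient tests, and non-pharmacological treatments: the unit costs will be established", goes on to drugs and lost productivity, and has no entry for transport.

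**Missing start date.** SAP section 5.2.9 applies to drug and non-drug IPF treatments. If the start date is missing and the treatment is ongoing, it imputes the cost of a full year, on the one further condition that IPF was diagnosed before 2018. It allows no other imputation apart from a rule for concomitant medication dates, and otherwise drops patients with missing values from the endpoint concerned. SAP section 5.2.5 takes time on drug treatment from the start and end dates. The visit flow chart in Protocol section 9.2.3 and the variable list in SAP section 5.2.7 both record these treatments at T0, T6 and T12.

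**Where the amounts go.** "Direct non-health costs will be calculated as the sum of transport costs, paid caregivers costs, orthoprosthetic material costs" are among the terms that make up one block of cost. Drug and non-drug treatments enter direct health cost. For society as a whole, SAP section 5.2.6.1 then says: "the total costs will be obtained as the sum of the direct health costs (without co-payment), direct non-health costs and indirect costs".

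**The concern.** The taxi rule contains two monetary terms, so it cannot be programmed to give a cost, and one of its inputs is not listed as collected. A programmer would have to guess the intended rule.

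The missing-date rule decides on a full-year charge from the year of diagnosis. That year does not show whether the treatment was in use at T0. The study holds a direct record of this at each visit, and the rule does not consult it. A treatment that began late in follow-up can therefore be charged for twelve months. A patient diagnosed in 2018 who was already treated at T0 gets no imputation and may be excluded from that endpoint, although the same record would bound the duration. Such patients can exist: data collection started on 29 November 2017 (SAP section 1.12) and enrolment was planned over six months (SAP section 1.8), so it runs into 2018.

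Both rules contribute to annual total cost, which is what the FVC groups are compared on.

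**Working it through.** The documents state no taxi or treatment cost total, so there is no figure to reproduce. The check is one of units and of months.

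**1. Units of the taxi rule.** Let n be the number of journeys, d the km per journey and c the unit cost in EUR per km. The SAP does not state the taxi unit cost; per km is assumed.

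- Natural units times unit cost: n × d × c, in km × EUR/km = EUR.
- As written: d × (total cost) × c, in km × EUR × EUR/km = EUR squared.
- If the total cost is itself n × d × c, the written rule equals the intended amount times d × c, the fare of one journey. That multiplier differs between patients and is not a fixed factor.

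Illustration with assumed values, 12 journeys of 20 km:

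| c (EUR/km) | intended | as written |
|---|---|---|
| 0.50 | 12 × 20 × 0.50 = 120 | 20 × 120 × 0.50 = 1,200 |
| 1.00 | 12 × 20 × 1.00 = 240 | 20 × 240 × 1.00 = 4,800 |
| 1.50 | 12 × 20 × 1.50 = 360 | 20 × 360 × 1.50 = 10,800 |

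The written rule can also reverse the order of patients. At an assumed 1 EUR/km, 10 journeys of 10 km against 4 of 20 km is 100 against 80 EUR as intended, but 10 × 100 = 1,000 against 20 × 80 = 1,600 as written. A rank test on transport cost would not be protected.

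**2. Why the km field must be defined.** Suppose the km field holds the total distance. Ten journeys of 20 km are 200 km. Replacing the cost by the number of journeys would then give 200 × 10 = 2,000 km, ten times too many.

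**3. Full-year charge against use between T0 and T12.** Treatment is ongoing at T12, and the overcharge is 12 minus the months of use. Nominal visits are at 6 and 12 months. The windows in Protocol section 9.2.3 put T6 at 4 to 8 months and T12 at 11 to 13. A negative figure is an undercharge.

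| First recorded at | use, nominal | overcharge, nominal | use, windows | overcharge, windows |
|---|---|---|---|---|
| T0 | 12 | 0 | 11 to 13 | −1 to 1 |
| T6 | 12 − 6 = 6, up to 12 | 0 to 6 | 11 − 8 = 3, up to 13 | −1 to 9 |
| T12 | 0 to 12 − 6 = 6 | 6 to 12 | 0 to 13 − 4 = 9 | 3 to 12 |

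For treatment first recorded at T12, the charge is thus at least 12/6 = 2 times the use at nominal visits, and at least 12/9 = 1.33 times over the windows.

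**4. Early end of follow-up.** A patient treated from T0 who leaves at month m with treatment ongoing is charged 12 months for m observed, an excess of 12 − m over observed use (6 months if m = 6).

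**5. Error if the start is placed midway between visits.** It is at most half the gap: 6/2 = 3 months at nominal visits; over the windows, 8/2 = 4 months (first recorded at T6) or 9/2 = 4.5 months (first recorded at T12).

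**The case against.** On the taxi rule, the best reply is that it is an obvious slip. The ambulance sentence uses trips, the protocol gives the general rule, and the literal formula would stall in programming for want of a fare. This largely stands: the intended method can be recovered, and a wrong published total is not the likely result. But the SAP nowhere states that method, and step 2 shows that swapping in the number of journeys is safe only once the km field is defined. The protocol's general reference to Spanish databases or similar studies does not identify a transport unit cost.

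On the missing date, the reply is that diagnosis before 2018 is a fair proxy for established treatment, that start dates are most likely to be missing for long-standing treatment, and that diary reconciliation (Protocol section 9.4) and eCRF checks (sections 9.6 and 9.8) limit missing dates. SAP section 5.2.9 also permits post-hoc imputation as a sensitivity analysis. Much of this stands. The charge is about right for treatment recorded at T0 and continued to T12, and that may be the commonest case, though the documents do not say so. Even so, the rule applies equally to treatment the record shows was absent at T0 or T6, and the sensitivity analysis is discretionary. SAP section 5.2.5 totals drug dose over the last six months, which sits uneasily with a full-year charge and does not override it.

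A reader might also infer from "multiplying the natural units of resource use (number of tests) by the unit cost of each outpatient test" that oxygen and ventilation will be costed as tests. The documents do not support this: section 5.2.6.2 prices non-drug treatments in their own right and section 5.2.9 gives them start dates, so costing by duration is implied.

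**Conclusion.** The taxi rule is wrong as written and must be corrected before it is programmed. A reader might infer that transport cost will be inflated by a known factor. That is not supported, because the formula does not yield euros and the fare it needs is not a listed input; the figures in step 1 rest on assumed journeys and prices.

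The full-year charge can overstate treatment cost when the T0 or T6 record, or an early end of follow-up, shows less than twelve months of treatment. At nominal visits the excess is 0 to 6 months if first recorded at T6 and 6 to 12 months if first recorded at T12. These ranges assume treatment continues to T12 without a break. A reader might infer that the rule always gives a wrong amount; it does not for treatment recorded at T0 and continued to T12, apart from up to a month either way from the visit window. For early leavers the excess is measured against observed use, and would shrink or vanish if all costs were scaled to a year, which the SAP does not spell out.

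Nor do the documents show that the comparison between FVC groups is biased. They give neither the number of patients affected, nor their distribution over the groups, nor the prices.

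**What to change.** - **SAP section 5.2.5, taxi.** Replace the formula with number of journeys × km per journey × unit cost per km, or total km × unit cost per km, according to what the eCRF km field holds. State which it is.
- **SAP section 5.2.6.2.** Add the transport unit cost, its unit and its source.
- **SAP section 5.2.9.** Replace the diagnosis-year condition with the visit record. Set the start to T0 if the treatment was recorded at T0. Otherwise use a date between the previous visit and the visit of first record, for example the midpoint, with the earliest and latest possible start as sensitivity analyses. Apply the same rule whatever the year of diagnosis.
- **Time charged.** Count only time within observed follow-up, and state whether it is capped at or scaled to twelve months, so that it agrees with the 12-month annual cost in section 5.2.4 and the cost per patient per year in section 5.2.8.

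The cost is a few sentences in the SAP, the matching code, a check of the km field and the lookup of a transport price. No new patient data are needed, since trips, kilometres and treatment by visit are already planned for collection. The downside is that the midpoint is an assumption; the earliest and latest starts bound it.
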